#### III. Compare the static and dynamic stability:

- a. To assess balance during functional activities the BERG balance scale will be used. This is a performance based tool, scored 0-56.
- b. To assess static balance, the single leg stance will be used. This will time in seconds, how long the subject can stand on one leg.
- c. To assess stepping and change of direction, the four square step test will be used. The subject will be required to walk in a sequence across canes arranged in four squares, timed in seconds.
- d. To assess dynamic falls risk and multitasking ability, the Dual task TUG will be performed. The patient will be given a second motor task while performing the TUG (e.g. carrying a glass of water)

# IV. Assess and compare patient perception and preference:

- a. To determine falls and near falls, subjects will fill out a self- reported Falls Efficacy scale (FES)
- b. To determine if cognition is a limitation the Mini-Mental State Exam (MMSE) will be administered.
- c. To determine prosthesis use and preference, the Prosthesis Evaluation Questionnaire (PEQ) will be given to the subject to fill out.
- d. These questionnaires will take between 5-20 minutes each to fill out.

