# Sub -hypothesis

- 3a: That C-leg will improve ambulation distance vs. mechanical knee
- 3b: That C-leg will improve time out of home vs. mechanical knee
- 3c: That C-leg will improve ability to use public transport vs. mechanical knee
- 3d: That C-leg will decrease gait aid vs. mechanical knee

Hypothesis 4: We hypothesize that the C-leg will significantly improve social integration as measured by CPI (Community Participation Indicators) in K2 Dysvascular subjects in comparison to mechanical knee.

Hypothesis 5: We hypothesize that the C-leg will significantly improve both static and dynamic balance as measured by Single Leg Stance (SLS), Timed Up and Go (TUG), BERG Balance Scale (BBS), Four Square Step test (FSST) and Dual task TUG tests in K2 Dysvascular subjects compared to a mechanical knee.

Hypothesis 6: We hypothesize that the C-leg will significantly improve self-reported measures in K2 Dysvascular subjects in comparison to mechanical knee.reduced falls measured by The Falls Efficacy Scale (FES), improved prosthesis use measured by The Prosthesis Evaluation Questionnaire (PEQ)

This study will be conducted at the Rehabilitation Institute of Chicago, [name].

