# 4) Research Methods: Study Design:

The study will have a randomized, repeated measures design. Due to the high rate of attrition we will randomize a total of 40 subjects, 20 into each of the groups below.

Group I

Mech Knee+Old Foot	C-leg + New Foot	C-Leg + New Foot	Mech knee + New Foot	Mech knee + New Foot
>6 months post TF prosthetic fitting	Acclimation	Assessment	Acclimation	Assessment
Duration	3 months	3 months	3 months	3 months
Data Collection	Monthly	Monthly	Monthly	Monthly

Group II

Mech Knee+Old Foot	Mech Knee + New Foot	Mech Knee +New Foot	C-Leg+ New Foot	C-Leg+ New Foot
>6 months post TF prosthetic fitting	Acclimation	Assessment	Acclimation	Assessment
Duration	3 months	3 months	3 months	3 months
Data Collection	Monthly	Monthly	Monthly	Monthly

All measures will be administered and data collected under the supervision of a licensed physical therapist.

- I. Assess and compare mobility in TF amputees:
  - a. To quantify community ambulation including time spent out of the home, use of public transport, GPS technology will be used. Subjects will be required to wear a GPS monitor on their belts during the day. This will track their activities in their homes and in the community.
  - b. To assess functional mobility the Amputee Mobility Predictor will be used. A standardized sequence of mobility tests with the prosthesis will be administered on the first pre-acclimation session. The patient will be scored out of 39.
  - c. To quantify fall risk and functional mobility the Timed Up and Go (TUG) test will be used. TUG is the time taken for the subject to get up from chair, walk 3 meters and sits down; measured in seconds.
  - d. To objectify the amount of steps in ADLs and functional mobility the Step Activity Monitor will be used. The subject will be given a monitor that he/she will have to wear around his/her ankle. This will record the number of steps.
  - e. To determine community and social participation, the Community Participation Indicators questionnaire will be used. It is a valid, new generation of self-report outcome measure for community participation. It will take 15-30 minutes to complete and will be administered in room 1771.
- II. Assess and compare gait distance and speed:

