# **Data Collection and Analysis**

Subjects will be screened and medical history and information relevant to why and when they received an amputation will be accessed from their medical records. Subjects will be explained the study design, procedures, tests, questionnaires and physical therapy visits asked to sign an informed consent prior to participating in the study. After subjects are randomized into two groups, they will be provided with a GPS device and a step activity monitor which will track their walking/mobility patterns at home and in the community for 4 weeks. When they return, over 1-2 visits, they will be assessed for a full battery of baseline outcome measures: six minute walk test (6 mwt), Amputee Mobility Predictor (AMP), Timed Up and GO (TUG), BERG balance test,. They will also be required to fill in self-report questionnaires for falls and the PEQ. They will then be fitted with the randomized prosthesis and new foot by a certified prosthetist. There will a period of acclimation for 3 months during which patients will be provided physical therapy with either the C-leg with a new foot or a mechanical leg with a new foot. Subjects will come for an average of two times a week for physical therapy training. The pre-training visits will include 1 for informed consent and GPS, 1-2 for evaluation and an additional 1-2 for prosthetic fit. The training sessions will be a maximum of 14. There will also be 1-2 reassessment visits. This will be repeated for the other prosthesis. There will be a maximum total of up to 45 visits. Subjects will be compensated \$40 per session for evaluation and assessments, prosthetic fittings and training sessions. This is the usual amount in similar studies and other studies at the Rehabilitation Institute of Chicago. The total compensation will be determined by the number of sessions that the subject completes while enrolled in the study. There will be 2 sessions allowed for a subject to be paid, even if they arrive but are unable to complete a session due to unscheduled issues (such as illness). However, if patients miss 3 or more consecutive visits, or experience a medical illness that may/may not require hospitalization, patients may have to be withdrawn from the study. Patients will be offered the additional service of adjustments for prosthesis/refining home exercise program in phone or in person, but they will not be compensated for these patient initiated services.

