The training will focus on providing both groups 1) strength training for upper limbs, core and lower limbs, 2) functional training, e.g. sit – stand, gait training on level surfaces, community ambulation and 3) cardiovascular and endurance training. The following 3 months there will be an assessment period for that particular knee and foot combination. In the course of the assessment period, patients will come in at regular intervals for data collection for the AMP and the 6 mwt. During the last 2 weeks of the assessment, patients will be given GPS devices for tracking their mobility data. At the end of 6 months there will be a crossover where patients with the mechanical leg will receive a new C leg + new foot and patients with the C leg will receive a mechanical leg + new foot. Once again, this will be followed by baseline testing, a period of 3 months acclimation with physical therapy sessions and a 3 month period of assessment where patients will come in for data collection. In the last 2 weeks, GPS data will be collected. The data collected will be analyzed for differences in outcome measures caused by the different prosthetic devices.

During the data collection process and the training sessions, a licensed physical therapist will be present to provide supervision and monitoring of the patient's vitals, signs and symptoms. During the sessions, subjects may be photographed or videotaped performing assessments, functional tasks, or exercising, with their consent. The photos and video recordings will not include the subjects face and if used for presentations or publications, will not identify the subject. The data collection and the training sessions will be terminated if the subjects expresses that he/she is unable/does not wish to participate. Subjects will be compensated \$40 per session. Payment will be in cash or by ClinCard per session, at the end of each session. RIC is moving away from using petty cash. During this transition period the subject may be paid in cash or by ClinCard. If a ClinCard is available when you come for the the study, you will be paid by card. If a ClinCard is not available, then you will receive cash payments.

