# Safety Assessment Risk and Injury

The primary risk in this study is the risk of falls, regardless of the prosthesis used. Fall prevention is a primary focus and the risk will be reduced by the use of harnesses, gait belts, assistive devices as needed and stand-by or contact guard assistance and supervision by researchers. All subjects will be initiated with testing and therapy sessions with simple activities, progressing on to more dynamic, complex activities when it is clear that they are safe and acclimated to the prosthesis being used. Other risks include muscle soreness from exercises during therapy sessions. To avoid this, subject will be provided with adequate rest periods and subjects will be monitored by questions regarding discomfort. Skin irritation from adjusting to a new socket fit can also be a risk. This risk will be minimized by regular check ups by a certified prosthetist, who will check for skin lesions/breakdowns.

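### The plan predicts fewer falls but names only the Falls Efficacy Scale to show it; no count or comparison of fall events between the knees is specified

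*Combined protocol and SAP*

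**What the plan says.** Two places tie falls to one scale. Hypothesis 6 (under Sub-hypothesis) expects "reduced falls measured by The Falls Efficacy Scale (FES"). Part IV, item a, of the Research Methods states: "To determine falls and near falls, subjects will fill out a self- reported Falls Efficacy scale (FES").

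Other places touch on falls without naming a count:

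- Data Collection and Analysis, with the baseline battery: "They will also be required to fill in self-report questionnaires for falls and the PEQ". The questionnaires are not named or described.
- Research Methods, part I, item c: "To quantify fall risk and functional mobility the Timed Up and Go (TUG) test will be used".
- Research Methods, part III, item d: "To assess dynamic falls risk and multitasking ability, the Dual task TUG will be performed".
- Safety Assessment Risk and Injury: "The primary risk in this study is the risk of falls, regardless of the prosthesis used". The section goes on to prevention. It does not say that falls are logged or tabulated by knee.

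For the assessment period, Data Collection and Analysis says that "patients will come in at regular intervals for data collection for the AMP and the 6 mwt"; it names no falls measure there. Statistical Analysis names a two-way repeated measures ANOVA and no model for counts or rates.

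**The concern.** A reduction in falls is a statement about events over time. It needs a definition of a fall, a count, a recall period and an exposure time on each knee. The plan gives none of these and assigns the claim to a scale whose name points to efficacy.

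The two can move apart. A person who feels more secure on a new knee may score better while falling just as often, or may walk more and fall more often. Under the current wording, the better score could be reported as fewer falls without any specified event data to support or contradict it. That matters more because falls are the risk the plan itself puts first.

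**Working it through.** **1. What each falls-related item can deliver.**

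| Item | Section | What it gives | Event count named? |
|---|---|---|---|
| Falls Efficacy Scale | Hypothesis 6; Research Methods IV.a | self-reported score | no |
| Falls questionnaires | Data Collection and Analysis | not described | no |
| TUG | Research Methods I.c | time in seconds, as fall risk | no |
| Dual task TUG | Research Methods III.d | TUG with a second task, as fall risk | no |
| Safety section | Safety Assessment | prevention measures | no |

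The two TUG tests do allow fall risk to be compared between knees. No row gives a specified comparison of fall events.

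**2. Visits at which a count could be taken.** Data Collection and Analysis plans up to 14 training sessions per knee during acclimation. For reassessment it says "There will also be 1-2 reassessment visits", and the sequence is repeated for the other prosthesis. The design tables show monthly data collection. If each month means a visit, that is 3 + 3 = 6 per knee, 3 of them in the assessment phase. A fall count is named at none of these.

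**3. Exposure.** Statistical Analysis gives 40 subjects and 30% attrition. 40 x (1 - 0.30) = 28 completers, and 28 / 0.70 = 40, so the attrition step agrees with the stated total. Each assessment phase lasts 3 months, so 28 x 3 = 84 person-months per knee.

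**4. Precision of a fall-rate ratio.** The documents give no fall rate. I assume 0.1, 0.25 and 0.5 falls per person-month. With E expected falls per knee, Poisson counts and a true ratio of 1.0, the 95% interval is exp(±1.96 x sqrt(2/E)).

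| Assumed rate | E = 84 x rate | 1.96 x sqrt(2/E) | 95% interval |
|---|---|---|---|
| 0.1 | 8.4 | 0.956 | 0.38-2.60 |
| 0.25 | 21 | 0.605 | 0.55-1.83 |
| 0.5 | 42 | 0.428 | 0.65-1.53 |

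**5. Power for a halving of falls (ratio R = 0.5).** Total falls over both knees are Poisson with mean E(1 + R). Given the total, falls on the C-leg are binomial with probability R/(1 + R) = 1/3, tested against 1/2 by the exact two-sided test at 0.05.

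| Assumed rate on the mechanical knee | Expected total, 1.5 x E | Power |
|---|---|---|
| 0.1 | 12.6 | 14.3% |
| 0.25 | 31.5 | 39.4% |
| 0.5 | 63 | 72.5% |

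For the plan's 90% power, the true ratio would have to be about 0.39 or lower at 0.5 falls per month and about 0.21 or lower at 0.25. At 0.1 per month, 90% is not reached even at a ratio of 0.01. Variation between periods within a subject beyond Poisson would widen the intervals and lower the power.

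**6. Who would be left out.** Withdrawal criteria list hospitalizations. A fall that leads to hospital can therefore end participation, and a rate computed in completers alone could miss the most serious falls.

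**The case against.** The best defence is that a short protocol need not describe every form. The falls questionnaires are mentioned in the plural and could include an event record; baseline testing is repeated at crossover; and the plan says outcome measures will be analyzed for differences between devices. All of this stands. A reader might infer that no fall events will be recorded, or that they will not be compared between the knees. The documents do not support that: they show only that no count or comparison is specified.

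A second defence is that the documents never describe the items of the Falls Efficacy Scale. That is also true. That it rates efficacy and not events is an inference from its name and its placement. The point does not depend on it, because no recall period, definition or event analysis is given whatever the items are.

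A third is that the safety section concerns prevention and says the risk applies whichever knee is worn. It does not call for a between-knee comparison, so it shows only that falls matter in this study.

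Finally, falls are one clause of the sixth hypothesis, while the stated primary aim is ADLs and community interaction, and a count would be underpowered even for a halving. This is a reason to put the rewording first and to treat the count as an estimate. It does not justify leaving a claim of fewer falls attached to an efficacy scale.

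**Conclusion.** The concern holds in this form: the claim about falls and its only named measure do not match, and no comparison of fall events between the knees is specified. The reading of the text is firm. It is a point that should be corrected, but it does not threaten the main aim of the trial.

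A fall count over the assessment phases could describe the difference but could not carry a test at the plan's own power. This rests on 28 completers, 3 months per assessment phase, Poisson counts and assumed fall rates that do not come from the documents.

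**What to change.** 1. Reword Hypothesis 6 and Research Methods IV.a so that the Falls Efficacy Scale supports a claim about falls efficacy only. This costs two lines of text.
2. State what the falls questionnaires in Data Collection and Analysis are and when they are given.
3. Define a fall and a near fall in advance. At visits already planned on each knee (training, data collection and reassessment), record the number of each since the last visit.
4. Report falls per person-month by knee, and the assessment-phase rate ratio with its 95% interval, labelled as an estimate and not a powered test.
5. Count all time on each knee up to withdrawal, including any fall that led to hospitalization and withdrawal, so that the analysis is not confined to completers. A subject who leaves before crossover contributes to one knee only, and the report should say how many do.

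The cost of items 3 to 5 is one or two questions per visit. The downsides are a wide interval, as shown above, and longer recall in the assessment phase if visits there are few. Recall is less of a problem during acclimation, when training sessions are frequent.

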# **Data Collection and Analysis**

Subjects will be screened and medical history and information relevant to why and when they received an amputation will be accessed from their medical records. Subjects will be explained the study design, procedures, tests, questionnaires and physical therapy visits asked to sign an informed consent prior to participating in the study. After subjects are randomized into two groups, they will be provided with a GPS device and a step activity monitor which will track their walking/mobility patterns at home and in the community for 4 weeks. When they return, over 1-2 visits, they will be assessed for a full battery of baseline outcome measures: six minute walk test (6 mwt), Amputee Mobility Predictor (AMP), Timed Up and GO (TUG), BERG balance test,. They will also be required to fill in self-report questionnaires for falls and the PEQ. They will then be fitted with the randomized prosthesis and new foot by a certified prosthetist. There will a period of acclimation for 3 months during which patients will be provided physical therapy with either the C-leg with a new foot or a mechanical leg with a new foot. Subjects will come for an average of two times a week for physical therapy training. The pre-training visits will include 1 for informed consent and GPS, 1-2 for evaluation and an additional 1-2 for prosthetic fit. The training sessions will be a maximum of 14. There will also be 1-2 reassessment visits. This will be repeated for the other prosthesis. There will be a maximum total of up to 45 visits. Subjects will be compensated \$40 per session for evaluation and assessments, prosthetic fittings and training sessions. This is the usual amount in similar studies and other studies at the Rehabilitation Institute of Chicago. The total compensation will be determined by the number of sessions that the subject completes while enrolled in the study. There will be 2 sessions allowed for a subject to be paid, even if they arrive but are unable to complete a session due to unscheduled issues (such as illness). However, if patients miss 3 or more consecutive visits, or experience a medical illness that may/may not require hospitalization, patients may have to be withdrawn from the study. Patients will be offered the additional service of adjustments for prosthesis/refining home exercise program in phone or in person, but they will not be compensated for these patient initiated services.

The training will focus on providing both groups 1) strength training for upper limbs, core and lower limbs, 2) functional training, e.g. sit – stand, gait training on level surfaces, community ambulation and 3) cardiovascular and endurance training. The following 3 months there will be an assessment period for that particular knee and foot combination. In the course of the assessment period, patients will come in at regular intervals for data collection for the AMP and the 6 mwt. During the last 2 weeks of the assessment, patients will be given GPS devices for tracking their mobility data. At the end of 6 months there will be a crossover where patients with the mechanical leg will receive a new C leg + new foot and patients with the C leg will receive a mechanical leg + new foot. Once again, this will be followed by baseline testing, a period of 3 months acclimation with physical therapy sessions and a 3 month period of assessment where patients will come in for data collection. In the last 2 weeks, GPS data will be collected. The data collected will be analyzed for differences in outcome measures caused by the different prosthetic devices.

During the data collection process and the training sessions, a licensed physical therapist will be present to provide supervision and monitoring of the patient's vitals, signs and symptoms. During the sessions, subjects may be photographed or videotaped performing assessments, functional tasks, or exercising, with their consent. The photos and video recordings will not include the subjects face and if used for presentations or publications, will not identify the subject. The data collection and the training sessions will be terminated if the subjects expresses that he/she is unable/does not wish to participate. Subjects will be compensated \$40 per session. Payment will be in cash or by ClinCard per session, at the end of each session. RIC is moving away from using petty cash. During this transition period the subject may be paid in cash or by ClinCard. If a ClinCard is available when you come for the the study, you will be paid by card. If a ClinCard is not available, then you will receive cash payments.

If the subject is issued a ClinCard, which is a specially designed debit card for clinical research, the funds will be loaded as appropriate. When a visit is completed, funds will be approved and loaded onto the card. The funds will be available within 1 day after being loaded and can be used at the subject's discretion. The subject will be issued one card for the duration of your participation. If your card is lost or stolen, please call [contact] or ask a coordinator for a replacement ClinCard.

Fees are incurred if used at an ATM (fees vary by location). However, if the card is used for in-store or online purchases via credit or debit, or presented to a bank teller, there are no associated fees and no expiration date.

If subjects wish to join RIC's gym to exercise to increasing endurance and fitness, we will provide them membership (with an RIC physician signing membership form) to RIC's Fitness Center and Sports Program (a \$35 cost that the study will pay to the Fitness Center for the subject). Subjects may be required to participate in a maximum of 45 sessions, although the maximum may not be needed for all subjects. The maximum

compensation is \$1800, although the total compensation will be determined by the number of sessions that the subject completes while enrolled in the study.

The data collected will be analyzed offline. All data and medical information of potential subjects will be locked in a file cabinet in the office of the PI. All study personnel listed will have access to the data and medical information. Subjects will be assigned a code when they are enrolled in the study. All GPS data will be analyzed by a researcher who is blinded to the subjects' identity. All data will be kept on computer hard-drives with accounts and passwords for security. Data will be stored in a locked file cabinet and on a secured-access computer. Data will not be destroyed. Only authorized individuals working directly in the study will have access to the computers.

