# 3) Hypotheses & Research Objectives and Purpose:

Central Hypothesis: We hypothesize that giving microprocessor knees (C-leg®), will significantly increase everyday function, social interaction, and quality of life in K2 Dysvascular subjects with transfemoral amputation in comparison to a standard mechanical knee (both FDA Class II exempt devices). The study will primarily aim to study the impact of the C-leg on ADLs and community interaction ADLs and function:

Hypothesis 1: We hypothesize that the C-leg will significantly increase every day physical activity measured using GPS tracked activity in K2 Dysvascular subjects in comparison to a mechanical knee.

Hypothesis 2: We hypothesize that the C-leg will significantly increase functional mobility in K2 Dysvascular subjects compared to a mechanical knee: increased stepping measured using Step Activity Monitor (SAM), increased gait speed and distance measured by Six Minute Walk Test (6MWT), increased mobility measured by the Amputee Mobility Predictor (AMP).

Hypothesis 3: We hypothesize that the C-leg will significantly increase community mobility measured using GPS technology in K2 Dysvascular subjects in comparison to a mechanical knee.

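### Blinding of the GPS researcher to knee and sequence is not stated; the plan's one blinding provision covers subject identity only

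*Combined protocol and SAP*

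**What the plan says.** **Blinding.** Data Collection and Analysis contains the only blinding statement in the text available for review: "All GPS data will be analyzed by a researcher who is blinded to the subjects". The object of the blinding, named in the next word, is identity. The statement stands among confidentiality provisions (subject codes, locked storage, passwords). The same paragraph gives all listed personnel access to data and medical information and makes no exception for the GPS researcher or for the allocation.

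**Role of GPS.** Section 3 states the aim: "The study will primarily aim to study the impact of the C-leg on ADLs and community interaction". Hypothesis 1 measures everyday physical activity by GPS. The other GPS hypothesis reads "Hypothesis 3: We hypothesize that the C-leg will significantly increase community mobility measured using GPS technology in K2 Dysvascular subjects". Section 4 also lists the step monitor and the Community Participation Indicators, which bear on the same aim.

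**GPS recordings.** There is a 4-week recording before the first fitting. Then, for each knee, "During the last 2 weeks of the assessment, patients will be given GPS devices for tracking their mobility data".

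**Order of events.** "After subjects are randomized into two groups, they will be provided with a GPS device and a step activity monitor". The 4 weeks of monitoring and the clinic baseline tests follow, and only after those: "They will then be fitted with the randomized prosthesis and new foot by a certified prosthetist".

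**The concern.** Hiding a name does not hide a device. A GPS file can be anonymous and still be recognisable as a C-leg or a mechanical-knee file, and the comparison of knees is what the trial is for. As written, the plan can be followed to the letter while the researcher knows which knee lies behind each file.

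The sub-hypotheses include time out of home and use of public transport. The plan gives no rules for deriving these from GPS tracks, so some judgement in processing cannot be ruled out. If that judgement leaned by knee, even unintentionally, it would distort the estimates for two hypotheses that serve the primary aim.

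A lesser matter is that the allocation exists for the whole baseline month, although it is not needed until fitting, and nothing says it is withheld. Subjects or therapists who knew which knee came first could influence the effort-dependent or self-reported first baselines.

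**Working it through.** **1. The plan's own figure.** Statistical Analysis gives power 0.90, two-sided 0.05, 30% attrition and 40 subjects. No effect size or SD is given, so 40 cannot be rebuilt from first principles. The attrition step is consistent: 40 × (1 − 0.30) = 28 completers, and 28 / 0.70 = 40. The blinding point does not depend on this figure.

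**2. Does the crossover remove knee-dependent processing error?** Let τ be the true C-leg minus mechanical difference, π₁ and π₂ the period effects, and b_C and b_M the average errors added when processing C-leg and mechanical files. Leave carryover aside. The within-subject C-leg minus mechanical difference has expectation:

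- Group I (C-leg first): τ + (π₁ − π₂) + (b_C − b_M)
- Group II (mechanical first): τ + (π₂ − π₁) + (b_C − b_M)
- Average of the two: τ + (b_C − b_M)

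The period effects cancel. The processing error does not, because it follows the knee in both groups. The documents give no value for b_C or b_M, nor any GPS standard deviation, so its size cannot be calculated.

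**3. Must period be hidden as well?** Section 4 puts 20 subjects in each sequence. For a researcher who does not know the sequence, the chance that a period-1 file is a C-leg file is 20/40 = 0.5, and the same holds for period 2. Period alone says nothing about the knee. Recording length does not reveal it either: the 4-week file marks only the pre-fitting recording, and both assessment recordings last 2 weeks. After the crossover the plan says "Once again, this will be followed by baseline testing", without saying whether GPS is repeated. If it is, that file would show the period, not the knee. Hiding knee and sequence is therefore enough.

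**4. Does randomising before baseline affect the knee contrast?** Let B be a subject's first baseline and Y₁, Y₂ the two assessment values. Even if change from that baseline were analysed, (Y₁ − B) − (Y₂ − B) = Y₁ − Y₂, so a disturbed B drops out. Statistical Analysis names prosthesis and testing session as factors and no baseline term. A period-1 comparison of change from baseline would be affected, but none is planned.

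**5. Does it affect the stated power?** Section 4 says "Due to the high rate of attrition we will randomize a total of 40 subjects", and Statistical Analysis likewise applies attrition to subjects randomised. Anyone lost between randomisation and fitting is already within the 30%, so the planned 28 completers are unchanged.

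**The case against.** **Silence is not disclosure.** A reader might infer that the GPS researcher is unblinded to the knee. The documents do not say so. They state what is hidden (identity) and are silent on knee and sequence. The sentence may have been written for privacy rather than masking. This limits the claim to something not stated. It does not remove the case for stating it, because nothing else in the text supplies the protection.

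**No subjective step is described.** Section 4 describes a belt-worn monitor that tracks activity, and no manual coding is mentioned. If every variable came from a fixed algorithm, knowing the knee would matter little. That is fair, but no algorithm or derivation rule is given either.

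**Illustrative error rates prove nothing here.** With 28 completers and a paired t-test standing in for the ANOVA, assumed shifts of 0.1, 0.2 or 0.3 SD of the within-subject difference would raise a two-sided 5% false-positive rate to about 8%, 18% or 33%. A reader might take these as the size of the problem. The shifts are invented, and the same figures would follow for any outcome, so they are no evidence about this trial.

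**GPS is not the whole primary aim.** The step monitor and the Community Participation Indicators bear on it too and are untouched by this gap. This stands.

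**Timing of randomisation.** A reader might infer that randomising before baseline biases the comparison or erodes power. Steps 4 and 5 show that neither follows under the planned analysis.

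**Limited gain.** Subjects will know their knee, and therapist-scored tests such as the AMP and Berg have no stated assessor blinding. Both are true. GPS files differ in that they can be masked cheaply after collection.

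**Conclusion.** The point holds in limited form. Blinding of the GPS researcher to knee and sequence is not stated, and the stated access rules would permit knowledge of both. Any knee-dependent processing error would pass undiminished into the C-leg versus mechanical contrast for Hypotheses 1 and 3. Whether such error would occur, and how large it would be, cannot be established from the documents. This is a cheap improvement worth making, not a demonstrated bias.

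The timing of randomisation is a minor note. It concerns the first baseline measures only. The conclusion that the knee contrast is unaffected rests on every subject using both knees and on the analysis having no baseline term, as Statistical Analysis describes. The conclusion on power rests on attrition being counted from randomisation, as the plan does. All of this covers the text available for review, from which the opening pages had been removed.

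**What to change.** **Main change, in Data Collection and Analysis.** State that the researcher who derives the GPS variables is blinded to identity, knee and sequence, and specify that:

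- GPS files carry a code with no knee or group label;
- this researcher has no access to the allocation or to records that reveal the knee, as an exception to the general access given to listed personnel;
- an existing staff member who does not process GPS data holds the key;
- unmasking takes place only after the derived GPS variables are locked.

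Masking the period, shifting dates and trimming the 4-week file are not needed once the sequence is hidden. True dates can stay in the files, which leaves season or transport timetables available if a GPS variable needs them.

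**Cost.** A little file recoding and a restriction on one researcher's data access. The change removes analyst bias only. It does not remove changes in subjects' behaviour that come from knowing which knee they wear.

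**Minor addition.** Keep the present order of events, but state that the sequence is withheld from subject, therapist and prosthetist until fitting. This needs no extra enrolment.
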